7 EARLY WITHDRAWAL OF SUBJECTS

7.1 When and How to Withdraw Subjects

Subjects will be withdrawn from the study in the following condition:

- Report of clinical significant adverse events felt to be related to study drug
- Failure of subject to adhere to protocol requirements
- Subject withdraw consent or their authorization to use their protected health information
- Subject is too ill to continue with the study procedure
- Deemed by the principal investigator to be in their best interest

Subjects discontinued from the clinical trial will be scheduled for a final evaluation. The investigator or sub-investigators will continue the care, consider alternative treatment or given appropriate treatment referrals for the subjects who withdraw from the study.

All subjects randomized into the study will be included in the final study analyses. Subjects are not dropped from all study activity unless they request not to be contacted or cannot be located for follow-up assessment. Subjects will be informed at the consent session that treatment may be discontinued due to:

- Intolerable side effects;
- Significantly abnormal laboratory values or confirmed with a repeat testing;
- Development or exacerbation of sexual dysfunction;
- Clinical deterioration for any reason or any clinical status that necessitates IP admission;

Reasons why subjects are discontinued from the clinical trial will be documented on the Study Termination Form, along with any referrals that are made. A final safety evaluation will be conducted as soon as possible on all randomized subjects who are discontinued. Every effort will be made to continue to collect data on every randomized subject for the entire study duration regardless of whether or not the subject continues to take study medication, assuming the subject has now withdrawn his/her authorization to obtain such information.

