11.3 Subject Population(s) for Analysis

Efficacy analysis will be performed on ITT basis. Any subject randomized into the study, regardless of whether they received study drug will be included into the analyses.

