While the safety of the subject always comes first, it is important to consider if unblinding the study therapy is necessary to ensure a subject's safety. If the SAE is confirmed due to the study therapy, the timeline of reporting is within 24 hours, however, in cases where unblinding was not associated with an SAE, the timeline of reporting is within 1 week.

Medical Monitoring

It is the responsibility of the Principal Investigator to oversee the safety of the study at his/her site. This safety monitoring will include careful assessment and appropriate reporting of adverse events as noted above, as well as the construction and implementation of a site data and safety-monitoring plan (see Section 10 Auditing, Monitoring and Inspecting). Medical monitoring will include a regular assessment of the number and type of serious adverse events.

Protection of Subjects

Complementing the safety measures noted above, additional procedures will be followed to protect the safety of the research subjects. Potential Subjects will be screened for medical illnesses that would preclude the use of methylphenidate. Specifically, these include known allergies to this agent. Subjects selected for the study will be evaluated daily while receiving study drug treatments. AEs will be monitored daily and a study physician will be available at all times to evaluate and treat adverse effects of the medication. On a daily basis, vital signs will be obtained. Significant AEs will result in exclusion from the study (see Clinical Trial Discontinuation Criteria). Subjects will be given a 24-hour emergency number they can call if necessary. The investigator or sub-investigators will clinically follow all subjects who are discontinued due to serious AEs until the AE resolves and becomes completely stable, unless a referral to another physician (i.e. specialist) is clinically indicated or requested by the subject.

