13 DISCONTINUATION AND REPLACEMENT OF SUBJECTS

13.1 Early Discontinuation of Study Drug

A subject may be discontinued from study treatment at any time if the subject, the investigator, or the Sponsor feels that it is not in the subject's best interest to continue. The following is a list of possible reasons for study treatment discontinuation:

- Subject withdrawal of consent (or assent)
- Subject is not compliant with study procedures
- Adverse event that in the opinion of the investigator would be in the best interest of the subject to discontinue study treatment
- Protocol violation requiring discontinuation of study treatment

- Lost to follow-up
- Sponsor request for early termination of study

If a subject is withdrawn from treatment due to an adverse event, the subject will be followed and treated by the Investigator until the abnormal parameter or symptom has resolved or stabilized.

All subjects who discontinue study treatment should come in for an early discontinuation visit as soon as possible and then should be encouraged to complete all remaining scheduled visits and procedures.

All subjects are free to withdraw from participation at any time, for any reason, specified or unspecified, and without prejudice.

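### Sections 7.1 and 12.2 withdraw or exclude subjects from the study for non-adherence or adverse events, contradicting the provisions elsewhere that subjects who stop study drug stay in follow-up

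*Combined protocol and SAP*

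**What the plan says.** **Wording that takes subjects out of the study.** The list in 7.1 is headed "Subjects will be withdrawn from the study in the following condition". Its entries include "Report of clinical significant adverse events felt to be related to study drug" and "Failure of subject to adhere to protocol requirements". In 12.2, under Protection of Subjects, the protocol states: "Significant AEs will result in exclusion from the study".

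**Wording that keeps them in.** Further down, 7.1 limits complete loss of contact to subjects who ask not to be contacted or cannot be found. It also calls for every effort to collect data over the whole study, on or off drug. Section 4.2 says much the same. Section 7.2 gives all assessments to subjects who are off drug and willing to attend. Section 13.1 lists non-compliance and adverse events as possible reasons for stopping study treatment, and says such subjects should attend an early discontinuation visit and "then should be encouraged to complete all remaining scheduled visits and procedures".

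**Analysis set.** Section 7.1 says "All subjects randomized into the study will be included in the final study analyses", and 11.3 agrees: "Any subject randomized into the study, regardless of whether they received study drug will be included into the analyses".

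**A reversed condition.** The sentence in 7.1 on continued data collection ends "assuming the subject has now withdrawn his/her authorization to obtain such information".

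**The concern.** The protocol does not keep apart two different events: stopping study drug and leaving the study. A coordinator whose subject misses doses or reports a significant adverse event can follow 7.1 and 12.2 and take him out, or follow 13.1 and keep him attending. Both courses comply with the protocol.

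The choice decides whether outcomes after stopping drug exist. Under the first course the week 2, 4 and 6 scores still due may never be collected, and the reason for the loss is tolerability or adherence, not chance. Section 11.2 handles missing scores through the mixed model under missing at random, which it calls often reasonable, and names no sensitivity analysis. The model would then fill in the missing course from what was observed before withdrawal and from subjects in the same arm who stayed. That describes the effect of assignment only if outcomes off drug resemble those observed. Section 13.2 says subjects who withdraw from study treatment are not replaced, so lost outcomes are not made up.

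**Working it through.** The point concerns consistency of text, so the main check sets the passages side by side.

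1. **Same reason, two consequences.** Non-adherence means withdrawal from the study in 7.1 but is only a possible reason for stopping treatment in 13.1. For adverse events, 7.1 requires clinical significance and suspected drug relation, 12.2 requires only significance, and 13.1 leaves the stopping of treatment to the investigator's opinion.

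2. **What follows each label.** For subjects withdrawn from the study, the first sentence of 7.2 names adverse event data for 14 days after the last drug. Its last sentence adds the End of Study assessments as final measures. For subjects who stop drug and are willing, 7.2 gives all assessments and 13.1 encourages all remaining visits. Section 13.2, on withdrawal from the study, mentions only an early discontinuation visit. The label therefore changes which efficacy scores are expected.

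3. **The withdrawal visit.** The Early Withdrawal Visit in 10.8 lists adverse events, diary, concomitant medication, examination, vital signs, urinalysis and ECG, but no CGI-SF, IIEF-15 or ASEX. Section 7.2 and the withdrawal column of Appendix 1 do provide for assessment of sexual function. Even the last efficacy measurement is thus uncertain.

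4. **Analysis set.** Sections 7.1 and 11.3 give the same rule: all randomised subjects are analysed. There is no conflict here.

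5. **The plan's own figure.** The only related figure is in 11.1: 90% power with 35 per group, effect size 0.5, 5% significance. With noncentrality 0.5 × √(35/2) = 2.09 and 68 degrees of freedom, a two-sample t-test has power 54.1% two-sided and 66.5% one-sided, so 90% is not reproduced. That is a separate matter. It enters here only as the baseline for step 6.

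6. **What can be said about size.** The documents give no discontinuation rate, no off-drug response and no comparative adverse event rate. For illustration only, assume:
   - a fraction q of the active arm stops and loses all benefit;
   - the placebo arm is unaffected;
   - no off-drug data are collected.

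   The effect of assignment is then 0.5 × (1 − q): 0.45 SD at q = 10% and 0.40 SD at q = 20%. A model that carries on the on-drug course returns about 0.5, an excess of 0.05/0.45 = 11% or 0.10/0.40 = 25%. For precision, losing 20% of week-6 scores in the active arm only (28 against 35) gives two-sided t-test power of 49.2%. Losing 20% in both arms (28 against 28) gives 45.1%. These power figures ignore the dropouts' earlier visits, which the mixed model would use.

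**The case against.** The strongest reply is that the protocol plainly intends follow-up to continue. Four sections say so, 7.2 is devoted to data collection for withdrawn subjects, and Appendix 1 schedules the sexual function interview at withdrawal. The 12.2 sentence sits in a paragraph about methylphenidate and daily evaluation, which does not fit this trial, and refers to discontinuation criteria under a title not found in the table of contents. It may be leftover text. Section 8.3.2.2 also allows dose reduction for intolerance, so an adverse event need not end in withdrawal.

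Much of this stands. A reader might infer that the withdrawal rules breach intention-to-treat, or that the plan removes outcome data selectively. The documents support neither: the analysis set is stated twice and consistently, and no passage orders outcome collection to stop or collected data to be discarded. A reader might also take the reversed authorisation clause as a real rule. It is an evident slip, since a site could not sensibly collect data only from people who had revoked authorisation.

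What the reply does not remove is the contradiction. The intention to follow up is expressed as effort and encouragement, while 7.1 and 12.2 are worded as mandatory. The promise not to drop subjects from all study activity does not secure the efficacy visits, and 10.8 omits the scales.

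**Conclusion.** The contradiction is real and should be reconciled. The withdrawal wording in 7.1 and 12.2 conflicts with the follow-up provisions in 4.2, later in 7.1, in 7.2 and in 13.1, and 10.8 is out of line with 7.2 and Appendix 1. The consequence is a risk: if staff apply 7.1 and 12.2 literally, CGI-SF, IIEF-15 and ASEX scores after stopping drug may be lost for reasons related to tolerability and adherence, leaving the mixed model to rely on an untested missing-at-random assumption.

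No size can be attached to this from the documents. The 11% to 25% excess in the working should not be read as an estimate. It rests wholly on assumed discontinuation confined to the active arm, total loss of benefit, and no off-drug data, the last of which runs against the protocol's stated intention. Greater loss on active drug is plausible but not shown, because 1.4.1 reports adverse events for the bupropion-treated patients only and gives no discontinuation rate.

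**What to change.** Reconcile 7.1, 10.8, 12.2 and 13.2 with 4.2, 7.2, 13.1 and Appendix 1, leaving the clinical stopping criteria as they are:

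- In 7.1 and 12.2, distinguish stopping study drug from leaving the study, and square the result with 13.2, which allows withdrawal from the study in the subject's best interest.
- State that subjects who stop study drug for non-adherence or an adverse event, and who are willing and able, remain in the study for the scheduled week 2, 4 and 6 efficacy scales. This must not oblige subjects who are too ill or unwilling.
- Add CGI-SF, IIEF-15 and ASEX to the Early Withdrawal Visit in 10.8, to match 7.2 and Appendix 1.
- In the 7.1 clause on authorisation, replace 'now' with 'not'.

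The cost is wording only, since the visits and scales are already planned. The change needs to be in place before subjects start stopping drug, because outcomes not collected on schedule cannot be recovered later.

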7.2 Data Collection and Follow-up for Withdrawn Subjects

Even though subjects may be withdrawn prematurely from the study all adverse event data will continue to be collected through 14 days from cessation of study drug (with the subject's permission). Subjects who have study drug discontinued for any reason, but are willing to complete study visits will have all assessments administered and collected. For the final measures, subjects will receive all assessments that were scheduled for the End of Study visit.

8 STUDY TREATMENTS

8.1 Method of Assigning Subjects to Treatment Groups

Up to 70 eligible patients will be randomly assigned to Bupropion Hydrochloride Sustained-Release or placebo treatment groups in a 1:1 ratio using a computer-generated table of random numbers through the use of the Randomization.com program. Subjects will be randomized to to Bupropion Hydrochloride Sustained-Release 150mg b.d. (n = 35) or placebo b.d (n = 35)

8.2 Blinding

Due to the objectives of the study, the identity of test and control treatments will not be known to investigators, research staff, or patients. The following study procedures will be in place to ensure double-blind administration of study treatments. Access to the randomization code will be strictly controlled. Besides, the packaging and labeling of test

and control treatments will be identical to maintain the blind. The study blind will be broken on completion of the clinical study and after the study database has been locked.

During the study, the blind may be broken only in emergencies when knowledge of the patient's treatment group is necessary for further patient management

8.3 Formulation of Test and Control Products

8.3.1 Description

Bupropion hydrochloride sustained-release (Wellbutrin SR™) tablets are biconvex purple film-coated with a white core.

8.3.2 Treatment Regimen

8.3.2.1 Route

The drugs are taken orally

8.3.2.2 Regime

Bupropion hydrochloride sustained-release started at 150mg on morning (0800) from day 1 to day 3. Dose increased to 150mg on morning (0800) and evening (1800) from day 4 onwards. The dose can be reduced to 150mg/day if patients are not able to tolerate a higher dose. The treatment continues until day 42.

8.4 Preparation and Administration of Study Drug

Study drug will be maintained and dispensed by the study coordinator. Tablets will be used as supplied, meaning that there is no further study drug preparation required. Study drug is administered orally.

8.5 Prior and Concomitant Therapy

All prior and/or concomitant medical therapy will be documented

Anxiolytic drugs (clonazepam, lorazepam, valium and alprazolam) and methadone are permitted for agitation, anxiousness or insomnia.

All other medication which can improve the sexual function except the study drugs are not permitted during the study.

8.6 Packaging and Labeling

The study drug will be repacked in the standard capsules by the research assistant who is not involved in the assessment of the study. The study drug and placebo will be packaged in sets of 11 (1 tablet per day for 3 days, followed by 2 tablets per day for 4 days.) for the first week. Subsequently, the study drug and placebo will be packaged in sets of 14 (2 tablets per day for 7 days.). Each packet (kit) of study drug will be labeled with the required FDA warning statement, the protocol number, a treatment number, and directions for patient use and storage.

8.7 Receiving, Storage, Dispensing and Return

8.7.1 Receipt of Drug Supplies

Upon receipt of the of the study drugs, an inventory will be performed and a drug receipt log filled out and signed by the person accepting the shipment. The designated staff will count and verify that the shipment contains all the items noted in the shipment inventory. Any damaged or unusable study drug in a given shipment (study drug or comparator) will be documented in the study files. The investigator will notify the Company of any damaged or unusable study treatments that were supplied to the investigator's site.

8.7.2 Storage

Stock study drug and drug packaged in patient kits within the research centre and study drug that has been dispensed to the Investigator, will be stored in a locked cabinets with climate control maintaining the temperatures within a range of 20°-25° C. Access to study drug within the research centre will be controlled by the staff, and access to study drug dispensed to the Investigator will be controlled by the Investigator and the Investigator's study staff.

8.7.3 Dispensing of Study Drug

All study drugs will be dispensed by investigator or their designated study staff.

8.7.4 Return or Destruction of Study Drug

An accurate and current accounting of the dispensing and return of study drug for each subject will be maintained on an ongoing basis by a member of the study site staff. The number of study drug dispensed and returned by the subject will be recorded on the Investigational Drug Accountability Record. The study monitor will verify these documents throughout the course of the study. . Any discrepancies noted will be investigated, resolved, and documented prior to destruction of unused study drug. After appropriate accounting, unused study drug will be destroyed on site with the date of this action documented in the study files.

8.8 Measures of Treatment Compliance

Subjects will be asked to keep a patient diary noting the day and date they take their study drug and any adverse events. They will be asked to bring their patient diary to each study visit along with all used and unused study drug containers. The research coordinator will conduct pill counts at each visit of all study subjects. Unused amounts will be documented. Proper drug dosing will be reviewed with subjects at each visit with clear instructions to take all study drugs as directed.

9 STUDY PROCEDURES AND GUIDELINES

A Schedule of Events representing the required testing procedures to be performed for the duration of the study is diagrammed in Appendix 1.

Prior to conducting any study-related activities, written informed consent must be signed and dated by the subject

9.1 Clinical Assessments

9.1.1 Concomitant Medications

All concomitant medication and concurrent therapies will be documented at Baseline/Screening and at Study Days and at early termination when applicable. Dose, route, unit frequency of administration, and indication for administration and dates of medication will be captured.

9.1.2 Demographics

Demographic information (date of birth, gender, race) will be recorded at Screening.

9.1.3 Medical History

Relevant medical history, including history of current disease, other pertinent respiratory history, and information regarding underlying diseases will be recorded at Screening.

9.1.4 Physical Examination

A complete physical examination will be performed by the investigator at Screening. Vital Signs, Body temperature, blood pressure, pulse and respirations will be performed after resting for 5 minutes at Baseline/Screening and at Study Days.

9.1.5 Adverse Events

Information regarding occurrence of adverse events will be captured throughout the study. Duration (start and stop dates), severity, outcome, treatment and relation to study drug will be recorded on the case report form (CRF).

9.2 Clinical Laboratory Measurements

9.2.1 Blood investigation

Approximately 20 ml (4 teaspoons) of blood will be collected at visit 0 (baseline) for a complete blood count (hemoglobin, white blood cell count, white blood cell differential, and platelet count), blood count, serum sodium, potassium, chloride, bicarbonate, creatinine, fasting glucose, aspartate aminotransferase (AST/SGOT), alanine aminotransferase (ALT/SGPT), total testosterone (TT), free testosterone (FT), estradiol (E2), luteinizing hormone (LH), prolactin, Hepatitis B, C and HIV. Approximately 5ml(1 teaspoon) of blood will be collected during visit 3 and 6 for liver function test: aspartate aminotransferase (AST/SGOT), alanine aminotransferase (ALT/SGPT).

9.2.2 Urinalysis

Urine will be obtained and tested for amphetamine, methamphetamine, marijuana and opioid in their urine by using F.A.C.T.S combo drug testing. The F.A.C.T.S combo drug testing is a competitive immunoassay utilizing highly specific reactions between antibodies and antigens for the detection of drugs which may be presented in the urine

specimens. During the testing, the urine specimen migrates upward by capillary action. If a drug is present in the urine specimen above the cut-off concentration, it will saturate all the binding sites of the antibody, and the colored line will not form in the test line region. To serve as a procedural control, a colored line will appear at the control line region. Hence, positive test will only have one line and negative test will have two lines on the test strip.

10 EVALUATIONS BY VISIT (REFER APPENDIX 1.)

10.1 Visit 0(Screening visit and Randomization)

Review the study with the subject and obtain written informed consent. Those who are willing to participate and consented will be screened for eligibility. A complete physical examination will be performed and blood will be collected for clinical laboratory tests. Urine will be collected for testing amphetamine, methamphetamine, marijuana and opioid. A Mini International Neuropsychiatric Inventory (MINI) will be administered to obtain DSM-IV diagnoses of opioid dependence and rule out other psychiatric disorders. MADRS, Malay version, OTI, WHOQoL-Brief, Malay version, Mal-GRIMS, CGI-SF, IIEF15, and ASEX will be completed. Eligible subjects will be scheduled for Visit 1 in 7 days.

10.2 Visit 1 (week 1)

Eligible subjects will be randomized and started either the study drug or placebo. Concomitant medications will be reviewed; abbreviated physical examination will be performed, vital signs will be recorded, Urinalysis for illicit drug and electrocardiography will be recorded. Eligible subjects will be scheduled for Visit 2 in 7 days.

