4.2 Procedure

All the male subjects who attended the methadone maintenance clinic will be approached. Screening data will be reviewed to determine subject eligibility. Subjects who meet all

inclusion criteria and none of the exclusion criteria will be entered into the study. Sexual dysfunction will be measured by CGI-SF, IIEF-15 and ASEX,

Seventy (70) of subjects will be randomized to one of two experimental treatments (35 subjects per group): bupropion hydrochloride sustained or placebo. Bupropion hydrochloride sustained or placebo will be initiated after screening and continued for 42 days of outpatient treatment. Efficacy will be take place at baseline, day 14(week 2), day 28(week four) and day 42 (week 6).

At the end of the 42 days, the continuation of treatment will be depends on the investigator's clinical judgment and End of Medication Evaluation will be perform. Every effort will be made to continue to evaluate all subjects who are randomized even if they decide to discontinue the medication.

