10.3 Visit 2 (week 2)

Any Adverse Experiences will be recorded. Subject diary for adverse experiences and dosing compliance will be reviewed. Concomitant medications will be reviewed; abbreviated physical examination will be performed, vital signs will be recorded, CGI-SF, IIEF15, and ASEX will be completed. Eligible subjects will be scheduled for Visit 3 in 7 days.

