10.5 Visit 4 (week 4)

Any Adverse Experiences will be recorded. Subject diary for adverse experiences and dosing compliance will be reviewed. Concomitant medications will be reviewed; abbreviated physical examination will be performed, vital signs will be recorded, CGI-SF, IIEF15, and ASEX will be completed. Eligible subjects will be scheduled for Visit 6 in 7 days.

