10.6 Visit 5 (week 5)

Any Adverse Experiences will be recorded. Subject diary for adverse experiences and dosing compliance will be reviewed. Concomitant medications will be reviewed; abbreviated physical examination will be performed, vital signs will be recorded, CGI-SF, IIEF15, and ASEX will be completed. Eligible subjects will be scheduled for Visit 6 in 7 days.

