10.7 Visit 6 (week 6) (end of study drug)

Any Adverse Experiences will be recorded. Subject diary for adverse experiences and dosing compliance will be reviewed. Concomitant medications will be reviewed; abbreviated physical examination will be performed, vital signs will be recorded, Urinalysis for illicit drug and electrocardiography will be recorded. Approximately 5ml(1 teaspoon) of blood will be collected for liver function test: AST(GOT) and ALT(GPT). CGI-SF, IIEF15, and ASEX will be completed. CGI-SF, IIEF15, and ASEX will be completed.

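### The day of first dose is contradictory: starting drug at Visit 1 puts the week 6 primary reading about 35 days into a course stated as 42 days

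*Combined protocol and SAP*

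**What the plan says.** **Start at Visit 1.** Section 10.1 ends Visit 0 with "Eligible subjects will be scheduled for Visit 1 in 7 days". Section 10.2 then states for Visit 1: "Eligible subjects will be randomized and started either the study drug or placebo". The Appendix 1 prescription row is ticked at Visits 1 to 6 and not at Visit 0. Section 10.2 lists no diary or adverse-event review. That first appears at Visit 2, in Section 10.3: "Subject diary for adverse experiences and dosing compliance will be reviewed".

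**Length of treatment.** Section 4.2 says drug "will be initiated after screening and continued for 42 days of outpatient treatment". Section 8.3.2.2 numbers its days from the first dose and runs to day 42. The Summary gives up to 7 days of screening, 42 of treatment and 14 of follow-up.

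**Timing of the readings.** Sections 4.2, 5.1 and 5.2 place efficacy at baseline and days 14, 28 and 42, without saying what day 0 is. The last visit is headed "Visit 6 (week 6) (end of study drug").

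**Hints of a Visit 0 start.** The heading of Section 10.1 reads "Visit 0(Screening visit and Randomization"), and Appendix 1 ticks treatment compliance and new symptoms at Visit 1.

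**Related loose ends.** Section 10.5, for Visit 4, says "Eligible subjects will be scheduled for Visit 6 in 7 days", passing over Visit 5. Section 10.6 has "CGI-SF, IIEF15, and ASEX will be completed" at week 5, and Section 10.4 does the same at week 3, but Sections 5.1 and 11.2 and Appendix 1 name only baseline and weeks 2, 4 and 6.

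**The concern.** The protocol has two clocks, one running from screening and one from first dose, and it does not say which one the week and day labels use. If drug starts at Visit 1, as the visit instructions say, the two clocks differ by a week at every reading.

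Staff who follow Section 10 and Appendix 1 would take the primary CGI-SF reading about 35 days into treatment and report it as the 42-day result. The last scheduled ECG and liver test would fall at the same point. If dosing nevertheless ran to day 42, the final week on drug would have no scheduled efficacy or safety reading at its end. If dosing stopped at Visit 6, the course would be a week shorter than stated.

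The Summary names IIEF-15 as primary and Section 5.1 names CGI-SF. Both are read at week 6, so the timing problem applies to either.

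**Working it through.** **Inputs.** Visits are 7 days apart (Sections 10.1 to 10.6, reading the Visit 6 booking in 10.5 as a slip for Visit 5). First dose is at Visit 1 (10.2, Appendix 1 prescription row). Treatment lasts 42 days (Summary, 4.2, 8.3.2.2). Readings are at days 14, 28 and 42 (4.2, 5.1, 5.2).

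**The plan's own figures.** The Summary total reproduces: 7 + 42 + 14 = 63 days. Day 42 for Visit 6 reproduces only when counted from Visit 0: 6 × 7 = 42.

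**Elapsed days.** Visit k is 7k days after Visit 0. Days since first dose are 7(k − 1) for a Visit 1 start and 7k for a Visit 0 start.

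| Visit | Days after Visit 0 | Since first dose, Visit 1 start | Since first dose, Visit 0 start | Scales in Section 10 | Scales in 5.1, 11.2, Appendix 1 |
|---|---|---|---|---|---|
| 0 | 0 | −7 | 0 | yes | yes |
| 1 | 7 | 0 | 7 | no | no |
| 2 | 14 | 7 | 14 | yes | yes |
| 3 | 21 | 14 | 21 | yes | no |
| 4 | 28 | 21 | 28 | yes | yes |
| 5 | 35 | 28 | 35 | yes | no |
| 6 | 42 | 35 | 42 | yes | yes |

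If the first dose is numbered day 1, as in Section 8.3.2.2, Visit 6 is treatment day 36; hence about day 35. A shorter screening period does not help, because Visit 1 to Visit 6 is 5 × 7 = 35 days regardless.

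**Shortfall with a Visit 1 start.** Week 2: 7/14 = 50%. Week 4: 7/28 = 25%. Week 6: 7/42 = 16.7%. Under the Section 8.3.2.2 regimen the week 2 reading follows about 7 − 3 = 4 days at target dose. Under the 7-day lead-in in the Summary it follows none.

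**Where day 42 would fall.** With 7 days of screening, treatment ends at study day 7 + 42 = 49. Neither Section 10 nor Appendix 1 has a visit there. Section 4.2 names an End of Medication Evaluation after 42 days, but neither schedule places it. True days 14 and 28 coincide with Visits 3 and 5, the visits whose scales the endpoint and analysis sections leave out.

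**Drug supply.** Assume one weekly kit per prescription tick, which the document does not state. Six kits hold 11 + 5 × 14 = 81 tablets, matching 3 × 1 + 39 × 2 = 81 over 42 days. The sixth kit is then handed out at Visit 6, so its 7 days come after the final reading. If the Visit 6 tick instead means continuation after the study, which Section 4.2 allows, five kits hold 11 + 4 × 14 = 67 tablets and cover 35 days. Neither case gives a day 42 visit.

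**Section 10.5 taken literally.** Visit 6 seven days after Visit 4 would be 21 + 7 = 28 days after first dose.

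**The case against.** The best counter-argument is that drug was meant to start at Visit 0. The 10.1 heading puts randomization there, Appendix 1 places Visits 1 to 6 in its on-treatment columns and checks compliance at Visit 1, and every section that states a number of days says 42. On that reading the schedule gives 14, 28 and 42 exactly. The prescription tick at Visit 6 also makes that row a weak marker of dosing dates.

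The hints are real, but this is the weaker reading. Section 10.2 says the opposite in plain words, and Appendix 1 prescribes nothing at Visit 0. Section 4.2 starts drug only once screening is done, and the Summary counts screening separately from treatment. The screening bloods are drawn at Visit 0, abnormal results exclude a subject (6.3), and eligibility must be signed off before medication is given (6.4). Dosing at Visit 0 would therefore need same-day results, for which the protocol makes no provision.

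A second argument is that the intended length is not in doubt, and that Section 4.2 plans an evaluation after 42 days which Visit 6 could be. That shows the intent, but Visit 6 cannot be both that evaluation and 35 days after first dose.

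Several points on the other side stand:
- The arms share the schedule, so the comparison between them is not biased.
- The document gives no time course, so nothing shows that a 5-week effect differs materially from a 6-week one.
- There is one centre, which limits divergent practice.
- The stated hypotheses concern week 6, so 17% is the shortfall that matters most.
- Section 11.2 lists the occasions from baseline, so baseline is a possible time origin. With a Visit 1 start, however, that origin lies 7 days before first dose.

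**Conclusion.** The concern holds. The protocol contradicts itself on when drug starts, and no section resolves it. On the better-supported reading, a Visit 1 start, the planned readings fall at 7, 21 and 35 days rather than 14, 28 and 42, and the primary reading is 7 days (17%) early. On the other reading there is no shift, but Section 10.2 and the prescription row are then wrong.

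The figure of 35 rests on weekly spacing as written and on treating the Section 10.5 booking as a slip. It does not depend on the kit assumption. The consequence is a misstated exposure and endpoint, not a biased treatment comparison. It should be fixed, but it does not invalidate the trial. Because Section 11.2 gives time no origin, the analysis plan cannot repair it later.

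**What to change.** - Make the drug-start visit day 0 and number every visit from it.
- Place the final efficacy, ECG and liver-test visit 42 days after first dose and name it as the End of Medication Evaluation.
- Align the 10.1 heading, Sections 10.2 to 10.7, Appendix 1 and the Summary with this. State whether the week 3 and week 5 scales are collected, and correct Section 10.5 to book Visit 5.
- In Section 11.2, define model time as days since first dose. Under a Visit 1 start the baseline scales sit at day −7, so say how that reading enters the model or repeat the scales before the first dose.
- Separately, reconcile the 7-day starting dose in the Summary with the 3-day one in Sections 8.3.2.2 and 8.6.

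The cost is an amendment, mainly to Section 10 and Appendix 1. The last visit moves a week later, or one visit at treatment day 42 is added if weekly contact is kept. The total stays within the 63 days per subject already planned (7 + 42 + 14).
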